- n. Blood and plasma samples will be collected for biobanking if specifically allowed by local EC/IRB; 1 tube of whole blood (prep D1) and 1 tube of plasma (prep B1) will be collected at the time points indicated in the Schedule of Activities. B1 and D1 samples will also be collected at the time of first response, where response is a major cytogenetic response for CP patients and a hematologic response for AP/BP patients when feasible. These additional biobank response samples should be obtained at the next scheduled visit if the next scheduled visit occurs within 2 months after the first response. If the next scheduled visit occurs >2 months after the first response, the sample should be collected at an unscheduled visit within 2 months after the first response, if feasible, unless this is the End of Treatment visit. If not collected on the designated collection day, collect at the next available time point when biospecimens are being collected in conjunction with a subject visit.
- o. End of Treatment visit should be done at Week 208 for those patients completing 4 years on bosutinib therapy, or at any time the patient meets any of the criteria for early discontinuation of bosutinib, whichever is earlier. Patients continuing to receive benefit from bosutinib at the time of study conclusion may switch to commercially available therapy. Note: 1 year = 52 weeks.
- p. Patients discontinuing treatment prior to 4 years from first dose will be followed for survival (telephone contact acceptable) until the patient has completed at least 4 years on study (from time of first dose) or sooner if the patient withdraws consent for disclosure of future information.
- q. Hepatitis B serology testing will be included in the screening tests and throughout the study as clinically indicated. Hepatitis B reactivation has been reported with Tyrosine Kinase Inhibitors (TKI's).

TABLE OF CONTENTS

TABLE OF CONTENTS.....	18
LIST OF TABLES	21
APPENDICES	21
1. INTRODUCTION	22
1.1. Indication.....	22
1.2. Background and Rationale	22
1.2.1. Therapeutic Options for CML	22
1.2.2. Bosutinib (BOSULIF®)	23
1.2.3. Study Rationale.....	28
2. STUDY OBJECTIVES AND ENDPOINTS.....	29
3. STUDY DESIGN.....	30
4. PATIENT SELECTION	31
4.1. Inclusion Criteria.....	31
4.2. Exclusion Criteria.....	33
4.2.1. Philadelphia Chromosome Negative (Ph-) CML Patients.....	34
4.3. Special Warnings and Precautions	34
4.4. Life Style Guidelines.....	35
4.5. Sponsor's Qualified Medical Personnel	36

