6.2. Study Period

The following procedures will be performed on treatment. Patients must be registered to the study after eligibility is confirmed within 3 days prior to receiving first dose of bosutinib.

Week 1 (Day 1, pre-dose and Day 7), Week 2, Week 3, Week 4 and Week 8 (± 1 day) on Day 7

- Hematology panel ([Appendix 9](#)); complete hematological assessment response;
- Liver function tests ([Appendix 9](#));
- Chemistry panel; including HbA1C, cholesterol, HDL, LDL, potassium, and magnesium, if clinically indicated ([Appendix 9](#));
- Coagulation tests ([Appendix 9](#));

- Urine or serum pregnancy test (for women of childbearing potential) (pre-dose Week1 Day 1 only) ([Appendix 9](#));
- Contraceptive check: patients of child-bearing potential will be required to affirm their use of 2 highly effective methods of contraception which will be documented in the patient's source document;
- Extramedullary disease assessment, if clinically indicated. Sites of extramedullary disease identified at screening should be followed during the course of treatment. Patients should be evaluated upon suspicion of new extramedullary disease;
- Hepatitis B serology testing, as clinically indicated;
- Patient diary card review ([Appendix 6](#));
- Bosutinib dispensation on Day 1.

Week 13, Week 26, Week 39, Week 52 (± 7 days), Week 78, Week 104, Week 130, Week 156, and Week 182 (± 21 days)

- Complete physical examination to include vital signs (sitting or supine blood pressure, heart rate and weight);
- Current smoking status.
- Extramedullary disease assessment, if clinically indicated. Sites of extramedullary disease identified at screening should be followed during the course of treatment. Patients should be evaluated upon suspicion of new extramedullary disease;
- Hepatitis B serology testing, as clinically indicated;
- ECG assessment, if clinically indicated;
- ECHO or MUGA scan assessment, if clinically indicated;
- Chest X-ray, if clinically indicated;
- ECOG Performance Status ([Appendix 8](#));

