7.1.1.1. Cytogenetic Response Assessment

Cytogenetic analysis will be performed by conventional cytogenetics from bone marrow, requiring at least 20 metaphases in order to evaluate number of Ph+ cells to determine cytogenetic response. Conventional cytogenetic assessment will be performed at scheduled visits until MMR is observed.

Only chromosome banding analysis of marrow cell metaphases will be used to assess the degree of CyR. Upon achieving CCyR by the conventional cytogenetic assessment, FISH of blood interphase nuclei with an appropriate probe (Dual-Color Dual-Fusion or Dual-Fusion FISH) could substitute for chromosome banding analysis of marrow cell metaphases for the assessment of maintenance of the CCyR (which is then defined by <1% BCR-ABL1-positive nuclei of at least 200 nuclei) until MMR is reached. Loss of CCyR using FISH will require resumption of bone marrow conventional cytogenetic assessment (unless the CML disease status is proven to be MMR by qRT-PCR).

For Ph- CML patients, conventional cytogenetic analysis will be performed only at screening and at the time of suspected progression and/or failure. Conventional cytogenetic assessment will be used to detect other potential cytogenetic abnormalities and molecular cytogenetic assessment (FISH) will be used to detect cryptic/variant translocations. Cytogenetic analysis will be conducted locally. Note: The cytogenetic assessment needs to be repeated at least 28 days later to confirm CCyR CML disease status for Ph+ CML patients (when the cytogenetic response is first observed in the absence of MMR, e.g. once CCyR is achieved by G-banding,

FISH is needed to confirm the achievement/maintenance of CCyR at least 28 days later). Loss of cytogenetic response must be confirmed by 2 assessments at least 4 weeks apart. (Note: if confirmation is lacking and the patient goes off treatment due to progressive disease, the assumption is that loss of cytogenetic response (CyR) is confirmed for this study; therefore, the confirmation of loss of CyR 4 weeks apart is not required in this clinical context).

Karyotypic abnormalities in Ph- subclones should be recorded. See [Appendix 11](#) for CyR criteria definitions.

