9.2.1. Analysis of Primary Endpoint

The primary efficacy analyses are the percentage of cumulative confirmed MCyR in CP 2nd and 3rd line patients, cumulative confirmed MCyR in 4th and later line patients and the cumulative confirmed OHR in AP and BP patients by 1 year of bosutinib treatment (Week 52) assessed from the local laboratory data. The primary analyses will be the percentage of cumulative confirmed MCyR (for CP Ph+ CML patients) and cumulative confirmed OHR

(for AP and BP Ph+ CML patients) by 1 year of bosutinib treatment (week 52). Confirmed MCyR will be defined as (1) the attainment of confirmed MCyR (CCyR or PCyR) by 1 year for patients entering the study without CCyR achieved on the previous TKI therapy or (2) the maintenance of confirmed CCyR (achieved under the previous TKI therapy) for at least 1 year after starting treatment with bosutinib or (3) at least MMR by 1 year and a deeper molecular response compared to baseline. Patients with baseline PCyR that do not achieve CCyR are included in the analysis but they would be counted as non-responders. Initial cytogenetic (in the absence of MMR) and hematologic responses must be confirmed by 2 consecutive assessments at least 28 days apart.

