3. INTERIM ANALYSES, FINAL ANALYSES AND UNBLINDING

There are no interim analyses planned for this study. The analysis for the primary objective will be done after all patients have completed one year of follow-up and all data through one year have been collected and processed. There will be one follow-up analysis when all study data are complete.

This is a single-arm, open-label study so unblinding is not required.

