6.1. Efficacy Endpoint(s)

Primary

- *Cumulative confirmed MCyR defined as Complete Cytogenetic Response (CCyR) or Partial Cytogenetic Response (PCyR) by 1 year (52 weeks) in 2nd and 3rd line CP patients.*
- *Cumulative confirmed MCyR by 1 year (52 weeks) in 4th and later line CP patients.*
- *Cumulative confirmed OHR defined as Complete Hematological Response (CHR) or Return to Chronic Phase (RCP) by 1 year (52 weeks) in AP and BP patients.*

The local cytogenetic assessments will be used for the primary endpoint analysis in CP patients. The local hematologic assessments will be used for the primary endpoint analysis in AP and BP patients.

Cumulative response is any response on-treatment up through Week 52 (based on the date of assessment) with a 4 week window (\leq Week 56). Response is confirmed for cytogenetic and hematologic with 2 consecutive responses at least 28 days apart. The date of confirmed response is the date of the first response. Cytogenetic and hematologic responses are defined in [Appendix 2](#) and [Appendix 1](#). MCyR is defined as a CCyR or PCyR. OHR is defined as CHR or RCP. To be considered a responder, the patient must have maintenance of baseline response for \geq 5 weeks for hematologic response or \geq 52 weeks for cytogenetic response or an improvement from baseline. Patients with PCyR at baseline must attain CCyR on-treatment to be counted as a cytogenetic responder. Patients with at least MMR and a deeper molecular response than baseline are counted as confirmed CCyR.

Secondary

- *Cumulative MCyR in CP, AP and BP patients.*
- *Cumulative confirmed OHR in AP and BP patients by line of therapy.*
- *Cumulative best response in CP, AP, and BP patients.*
- *MCyR at 3, 6, 12, 18, and 24 months in CP, AP, and BP patients.*
- *Confirmed OHR at 3, 6, 9, 12, 18, and 24 months in AP and BP patients.*
- *Cumulative confirmed CHR.*
- *Cumulative MMR in CP, AP, and BP patients.*
- *Duration of CCyR.*
- *Duration of MMR.*

The local cytogenetic assessments will be used for the secondary endpoint analyses for all patients. The local hematologic assessments will be used for the secondary endpoint analyses for all patients. *Molecular assessments will be performed at a central laboratory. Endpoint analysis for molecular response will be carried out by independent central analysis.*

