8.2.1. Analysis of Primary Efficacy Endpoints

The response rate analyses are based on the evaluable analysis set for Ph+ CML patients only. The primary efficacy analysis is the percentage of responders by Week 52, done separately for:

- Confirmed MCyR for combined CP2L and CP3L;
- Confirmed MCyR for CP4L;
- Confirmed OHR separately for AP and BP.

Any patient not demonstrating a response by Week 52 is deemed a non-responder.

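### For CP patients entering in CCyR, the 52-week maintenance rule does not fit the Week 52 visit window: read literally, a compliant early visit makes a patient still in CCyR a primary non-responder

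*Protocol*

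**What the plan says.** **The rule.** Protocol 9.2.1 gives three routes to confirmed MCyR in chronic phase. Route (2), for patients who enter in CCyR, is "the maintenance of confirmed CCyR (achieved under the previous TKI therapy) for at least 1 year after starting treatment with bosutinib". Footnote o of Table 1 sets the length: "Note: 1 year = 52 weeks". SAP 6.1 states the rule as keeping the baseline response for at least 52 "weeks for cytogenetic response or an improvement from baseline". Route (3) is a molecular response of at least MMR that is also deeper than at baseline; the SAP counts it as confirmed CCyR.

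**The cut-off.** SAP 6.1: "Cumulative response is any response on-treatment up through Week 52 (based on the date of assessment) with a 4 week window", written out as no later than Week 56. SAP 8.2.1 adds the default: "Any patient not demonstrating a response by Week 52 is deemed a non-responder".

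**The visits.** Protocol 6.2 schedules "Week 13, Week 26, Week 39, Week 52" with 7 days either side. After that come Week 78 and the later visits, with 21 days either side.

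**Neighbouring rules.** SAP 6.1 gives landmark responses a window on both sides, and SAP 8.2.2 lets responses before and after a missed landmark visit fill the gap. Both are written for secondary landmark endpoints only. Protocol 7.1.1.1 says: "Loss of cytogenetic response must be confirmed by 2 assessments at least 4 weeks apart".

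**The concern.** The 52-week threshold sits in the middle of the window in which the Week 52 visit may be held. A visit a few days early complies with the schedule but shows slightly less than 52 weeks, and no tolerance is written on that side. A patient who enters in CCyR cannot improve cytogenetically, so without a deeper molecular response, primary status rests on the maintenance rule.

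Such patients are expected. Eligibility includes TKI-intolerant patients and waives the screening marrow for those in MMR, and the evaluable set in SAP 5.4 admits baseline CCyR by FISH and baseline MMR. Two careful programmers could therefore report different primary rates from the same data. The study is descriptive, so what is at stake is a reported estimate and not a test. That estimate does, however, belong to the study required for converting the conditional EU authorisation.

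**Working it through.** **Inputs.** Maintenance of at least 1 year from start of bosutinib (Protocol 9.2.1); 1 year = 52 weeks (Table 1, footnote o); Week 52 ± 7 days and Week 78 ± 21 days (Protocol 6.2 and Table 1); primary cut-off Week 56 (SAP 6.1); 106 patients in the 2nd/3rd-line cohort (Protocol 1.2.3); at least 45 in the 4th-or-later-line cohort (Protocol 9.1).

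**Assumptions.** Week 52 is day 364. The convention that a visit falls on Day 7 of its week is written only for Weeks 1–8. Elapsed time uses the count with one day added that SAP 6.1 gives for its time-to-event endpoints, so an assessment on day d shows d days.

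**The plan's own figures.** 52 + 4 = 56 weeks = 392 days, as stated. The SAP's landmark examples also reproduce: 13 ± 2 gives Weeks 11–15, and 78 ± 4 gives Weeks 74–82. So does the precision statement in Protocol 9.1: √(0.25/45) = 0.0745, within the stated 0.075.

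**Step 1: the visit window.** 52 × 7 = 364; 364 − 7 = 357 and 364 + 7 = 371. That is 15 compliant days.

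**Step 2: weeks shown at the visit.** Day 357: 357/7 = 51.00. Day 363: 363/7 = 51.86. Day 364: 364/7 = 52.00. Days 357–363 fall short, which is 7 of 15 compliant days (47%). This is a share of permitted days, not of patients.

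**Step 3: other day conventions.**

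| Nominal Week 52 | Days short, one day added | Days short, plain date difference |
|---|---|---|
| Day 364 | 357–363 (7) | 357–364 (8) |
| Day 365 | 358–363 (6) | 358–364 (7) |
| Day 358 | 351–363 (13) | 351–364 (14) |

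The exact days move, but under each convention some compliant visits fall short.

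**Step 4: can a later scheduled visit help?** Week 78 = 78 × 7 = day 546; 546 − 21 = day 525 at the earliest. The cut-off is day 392, and 525 − 392 = 133 days. No scheduled cytogenetic assessment falls between the early Week 52 visit and the cut-off.

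**Step 5: weight of one patient.** 100/45 = 2.2 points and 100/106 = 0.94 points. Both counts cover all disease phases, so with smaller chronic-phase denominators each patient weighs more. For scale, the exact 95% interval at 22/45 runs from 33.7% to 64.2%, about ±15 points.

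**The case against.** The strongest answer is that the literal reading is too strict. Protocol 9.2.1 itself equates one year of treatment with Week 52, which is a scheduled visit with a window. A cumulative endpoint needs only an upper limit, so the absence of an early tolerance need not mean that early visits fail. Loss of cytogenetic response has to be confirmed, and a patient in CCyR at a compliant Week 52 visit has no recorded loss. An analyst could reasonably treat maintenance as absence of confirmed loss. This stands as a sensible way to program the rule, but neither document adopts it for this endpoint, and both write the requirement as a minimum length.

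The group is also narrow, and that stands. The patient must enter in CCyR, remain in it, be seen early, lack an MMR deeper than baseline, and have no unscheduled cytogenetic assessment or MMR-imputed CCyR from day 364 to day 392.

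Two further inferences are tempting but unsupported. First, a reader might think that CCyR at Week 78 could complete the year, since route (2) has no upper limit of its own. The SAP effectively excludes this. It stops the primary at Week 56, scores by Week 52, says in the COVID-19 paragraph of 8.2.2 that the primary uses data up to Week 52, and schedules the analysis in section 3 "after all patients have completed one year of follow-up and all data through one year have been collected and processed". Second, a reader might think that the start of the 52 weeks is open because the SAP 6.1 sentence gives none. Protocol 9.2.1 counts from the start of bosutinib, and SAP section 1 describes the requirement as one year on treatment.

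Finally, loosening the rule now would come after all patients had passed Week 52 in an open-label study. That caution stands, and the fix has to respect it.

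**Conclusion.** The point holds as a mismatch between the primary rule and the visit schedule. Applied as written, the rule makes a patient in CCyR at a compliant early Week 52 visit a non-responder on the booking date alone, unless route (3) or another assessment by day 392 applies. Under that reading the error can only lower the MCyR rate. The documents do not show that the analysis was or will be programmed this way; they leave it unsaid.

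The effect is probably small and cannot be sized, because neither the number entering in CCyR nor the actual visit days are given. A reader might take the earlier phase 1/2 study in Protocol 1.2.2 as a ceiling, using CCyR newly achieved or maintained minus CCyR attained: 46 − 43.0 = 3.0 points in imatinib-resistant and 54 − 42.5 = 11.5 points in imatinib-intolerant patients. It is not one. Those were second-line patients under a maintenance rule that is not given, while this trial also enrols later lines and patients already in MMR.

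The specific days 357–363 rest on Week 52 being day 364 and on the count with one day added. The per-patient weights rest on all-phase counts, one a minimum and the other the figure when the amendment was written. No hypothesis test is affected. The clarification is worth making because it is cheap and concerns the primary endpoint.

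**What to change.** In SAP 6.1, with matching wording in Protocol 9.2.1:

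- Restate that the 52 weeks run from first dose, as the protocol already says.
- Add a window-based result. Maintenance is met by CCyR (by banding, by FISH or imputed from MMR) at the Week 52 assessment within its protocol window and no later than Week 56, with no earlier confirmed loss.
- Report it beside the literal result of at least 52 weeks, with the number of patients whose classification changes.
- Say which result is the main one, and how a CCyR entrant with no Week 52 assessment is scored.

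If the primary analysis has already been run, the minimum is to document which reading was used and give the number reclassified under the other.

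**Cost.** One extra table row and a few sentences of text. Section 9 of the protocol requires a major change to the primary definition or its analysis to be reflected in an amendment. The window-based result counts some patients with 51 to under 52 observed weeks, and it would be added after every patient had passed Week 52. For that reason both results must be shown.

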9.2.2. Analysis of Secondary Endpoints

Percentages for the following secondary endpoints will be calculated:

- Cumulative MCyR anytime on treatment in the CP, AP and BP Ph+ CML patient populations.
- Cumulative confirmed OHR anytime on treatment in the different advanced phase (AP, BP) Ph+ CML patient populations by lines of prior of therapy.
- Cumulative best response anytime on treatment in the different CP, AP, and BP Ph+ CML patient populations, also in the 4th- or later-line treatment setting. The hierarchy to assess for best response is MR4.5, MR4, MMR, CCyR, PCyR, CHR, and OHR.
- Landmark MCyR at 3, 6, 12, 18, and 24 months in the different CP, AP and BP Ph+ CML patient populations.
- Landmark confirmed OHR at 3, 6, 9, 12, 18, and 24 months in the AP and BP Ph+ CML patient populations.
- Cumulative confirmed CHR anytime on treatment in the CP, AP and BP Ph+ CML patient populations.
- Cumulative MMR anytime on treatment in the CP, AP and BP Ph+ CML patient populations.
- Duration of CCyR.
- Duration of MMR.

Analyses of hematologic and cytogenetic response will be based on the data from the local laboratory assessment. Analyses of molecular response will use the data from the independent central laboratory.

Duration of response is defined as the interval from the date of first on-treatment response to the date of confirmed loss of response, death within 28 days of last dose, or treatment discontinuation due to disease progression. Responders without loss of response will be censored at the last valid assessment for the respective endpoint.

The secondary time-to-event endpoint duration of response will be summarized using the Kaplan-Meier method or by cumulative incidence, whichever is more appropriate, depending on the competing risks (e.g., treatment discontinuation without disease progression in the analysis).

9.3. Analysis of Other Endpoints

OS or survival time is defined as the interval from the date of first dose of bosutinib to the date of death due to any cause. Patients not known to have died will be censored at the last known alive date. The OS distribution up to at least 4 years will be provided.

PFS is the interval from the date of first dose of bosutinib until the earlier date of disease progression or death from any cause. Patients without PFS events will be censored at the last evaluation date. The PFS distribution up to at least 4 years will be provided.

The exploratory time-to-event endpoints of OS and PFS will be summarized using the Kaplan-Meier method or by cumulative incidence, whichever is more appropriate, depending on the competing risks (e.g., treatment discontinuation without progression in PFS analysis).

For Ph- CML patients, cumulative best response anytime on treatment will be provided. The hierarchy to assess for best response is MR 4.5, MR4, MMR, MR2, MR1, CHR, and OHR.

The percentage of patients with baseline and emergent Bcr-Abl kinase-domain mutations, along with the specific types of mutations, will be summarized.

The FACT-Leu will be scored according to the respective user's guides and validation papers. Summary statistics of the Functional Assessment of Cancer Therapy-Leukemia (FACT-Leu) quality of life questionnaire will be calculated at baseline and approximately every 3 months for the first year, and every 6 months during year 2, 3 and 4 of treatment on study. The mean and 95% CI and median of the observed scores and the changes from baseline will be reported for the FACT-Leu, individual domains, and items.

9.4. Safety Analysis

AE incidence rates will be described both with and without regard to causality. The frequency of occurrence of overall toxicity, categorized by toxicity grades (NCI CTCAE v4.0), will be described. Listings of laboratory test results collected at baseline and during the study will be generated and descriptive statistics summarizing changes in laboratory tests over time will be presented.

The safety analyses will be based on the FAS.

